6MWD, 6-minute walk distance; AE, adverse event; AEoSI, adverse event of special interest; ECG, electrocardiogram; hsCRP, high-sensitivity C-reactive protein; KCCQ, Kansas City Cardiomyopathy Questionnaire; HF, heart failure; IL-6, interleukin 6; IP, Investigational Product; LAVI, left atrial volume index; LV-GLS, left ventricular global longitudinal strain; LVMI, left ventricular mass index; NT-proBNP, N-terminal pro-brain natriuretic peptide; TSS, total symptom score.

For Tertiary/Exploratory objectives and endpoints descriptions, see Section 3 of the protocol.

Overall Design

This is a sequential, randomised, double-blind, placebo-controlled, multi-centre Phase 2b/3 study to evaluate the efficacy and safety of AZD4831 in participants with HF with LVEF > 40%. AZD4831 will be administered in addition to optimal background therapy for co-morbidities for 48 weeks (Part A), and 24, 36 or 48 weeks (Part B). In Phase 2b (Part A), approximately 660 participants will be randomised in 3 treatment groups in 1:1:1 allocation, and will receive once-daily oral dose of either AZD4831 2.5 mg, AZD4831 5 mg, or placebo. In Phase 3 (Part B), approximately 820 participants will be randomised in 2 treatment groups in 1:1 allocation, and will receive once-daily oral dose of AZD4831 (either 2.5 mg or 5 mg based on interim results of Part A) or placebo. Randomisation in both phases will be stratified by neutrophil count.

Disclosure Statement: This is a double-blind (participant, investigator, and sponsor blinded) parallel group treatment study with 3 arms in Part A and 2 arms in Part B.

Number of Participants:

	Part A	Part B
Enrolled	Estimated 1100 participants	Estimated 1350 participants
Randomised	Estimated 660 participants	Estimated 820 participants
Participants with complete safety data	Estimated 600 participants	Estimated 745 participants

Note: “Enrolled” means a participant's, or their legally acceptable representative's, agreement to participate in a clinical study following completion of the informed consent process. Potential participants who are enrolled for the purpose of determining eligibility for the study, but are not randomised in the study, are considered “screen failures”, unless otherwise specified by the protocol.

The study will be conducted in approximately 180 sites and approximately 15 countries.

Intervention Groups and Duration:

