In Part A, participants will undergo a screening period of up to 4 weeks, followed by randomisation across 3 different treatment arms. Eligible participants will be randomised at a 1:1:1 ratio and dosed orally once daily. The planned treatment arms are AZD4831 2.5 mg, AZD4831 5 mg, and placebo. Participants will receive either AZD4831 or placebo for 16 weeks and then continue into a safety extension, during which they will receive an additional 32 weeks of the intervention (AZD4831 or placebo, as per their assigned arm during randomisation). A final follow-up visit (end of study visit) will occur at 52 weeks from randomisation. In the event that randomisation to the AZD4831 5 mg treatment arm is stopped during the study in either the whole study or in a country or specific ethnic population due to safety, the remaining participants in that cohort would be randomised at a 2:1 ratio to AZD4831 2.5 mg or matching placebo.

In Part B, participants will undergo a screening period of up to 2 weeks, followed by randomisation across 2 treatment arms. Eligible participants will be randomised at a 1:1 (AZD4831:placebo) ratio and dosed orally once daily. The planned treatment groups are AZD4831 at the dose selected based on Part A, and placebo. Participants will be treated for 24, 36 or 48 weeks, depending on when in time they were enrolled. The date of the last participant randomised in the study will determine the treatment period for patients who are still in the study. When the last patient is randomised, the end of the 24 week treatment period will be known; therefore the end of treatment date for all other ongoing participants will be scheduled in advance to occur at 24, 36 or 48 weeks. Consequently, earlier enrolment will allow a longer treatment period, whereas later enrolment will restrict the treatment period to 24 weeks. Participants will be treated for a minimum of 24 weeks to allow sufficient time for

efficacy evaluation, and a maximum of 48 weeks to assess longer-term safety and effect of the IP. A final end of study visit will occur 4 weeks after the final dose.

Participants can be randomised only once in the study; therefore, participants who were randomised into Part A cannot be included in Part B.

Data Monitoring Committee: Yes

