3 OBJECTIVES AND ENDPOINTS

3.1 Part A

The following information in Table 4 relates to the objectives of Part A of the study. The dose in Part B will be the dose with optimal risk-benefit profile based on the data in Part A.

Table 4 Objectives and Endpoints – Part A

Objectives	Endpoints/Variables
Primary	
To evaluate the effect of AZD4831 on KCCQ-TSS	KCCQ-TSS change from baseline at 16 weeks compared with placebo
To evaluate the effect of AZD4831 on 6MWD	6MWD change from baseline at 16 weeks compared with placebo
Secondary	
To evaluate the effect of AZD4831 on KCCQ-TSS	KCCQ-TSS change from baseline at 24 and 48 weeks compared with placebo
To evaluate the effect of AZD4831 on 6MWD	6MWD change from baseline at 24 and 48 weeks compared with placebo
To evaluate the effect of AZD4831 on NT-proBNP	NT-proBNP change from baseline at 16, 24, and 48 weeks compared with placebo
To evaluate the effect of AZD4831 on echocardiographic parameter LV-GLS	LV-GLS change from baseline at 16 and 24 weeks compared with placebo
To evaluate the effect of AZD4831 on echocardiographic parameter LAVI	LAVI change from baseline at 16 and 24 weeks compared with placebo
To evaluate the effect of AZD4831 on echocardiographic parameter LVMI	LVMI change from baseline at 16 and 24 weeks compared with placebo
To assess the pharmacokinetics of AZD4831	Concentrations will be summarised by timepoint and dose level
To evaluate the effect of AZD4831 on inflammatory biomarkers	hsCRP and IL-6 change from baseline at 16, 24, and 48 weeks compared with placebo

Table 4 Objectives and Endpoints – Part A

[figure not shown]
Objectives	Endpoints/Variables
Safety	

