6.3 Measures to Minimise Bias: Randomisation and Blinding

All participants will be centrally assigned to randomised study intervention using an IRT/RTSM. This computerised randomisation procedure will ascertain allocation concealment and will assign the participants 1:1:1 to two dose levels of AZD4831 or matching placebo in Part A and 1:1 to AZD4831 or matching placebo in Part B. For Part A, in the event that randomisation to the AZD4831 5 mg treatment arm is stopped during the study due to safety in either the whole study or in specific countries or ethnic populations, the remaining participants in that cohort will be randomised at a 2:1 ratio to 2.5 mg AZD4831 or matching placebo.

The randomised study population will be capped by neutrophil count, 6MWD and KCCQ-TSS in both Part A and Part B. The capping will consist of:

- The proportion of participants having neutrophil count $> 4 \times 10^6/\text{mL}$ at Screening will be 60%-80%
- A maximum of 25% of the participants can have 6MWD ≥ 350 and ≤ 400 meters at randomisation visit.
- A maximum of 30% of the participants can have KCCQ-TSS > 80 and ≤ 90 at randomisation visit.

LVEF value at screening and atrial fibrillation/flutter status on ECG at Screening (Visit 1) may also be capped in the IRT/RTSM to avoid over- or under-representation of these participant subgroups.

The randomisation will be stratified by neutrophil count in both Part A and Part B.

The study will be blinded to both participants and Investigators/site staff as well as to the sponsor (designated sponsor personnel will be unblinded as part of DRC and URC in Part A as described in Appendix A 5). The IRT/RTSM will provide to the Investigator(s) the kit identification number to be allocated to the participant at the dispensation visit. Study intervention will be dispensed at the study visits summarised in the SoA (See Section 1.3). Routines for this will be described in the IRT/RTSM user manual that will be provided to each centre.

The randomisation code should not be broken except in medical emergencies when the appropriate management of the participant requires knowledge of the treatment randomisation. The investigator documents and reports the action to AZ, without revealing the treatment given to participant to the AZ staff.

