9.4.2 Efficacy

9.4.2.1 Primary Endpoint(s)

The primary efficacy endpoints are KCCQ-TSS and 6MWD and the primary efficacy variables are change from baseline in KCCQ-TSS and 6MWD at 16 weeks for Part A and at 24 weeks for Part B.

All primary variables will be analysed using ANCOVA with baseline and treatment group as covariate, and will be adjusted for the stratification factor for neutrophil count (Part A and Part B), comparing the AZD4831 doses versus placebo. For Part A, both single doses alone, and both doses pooled, will be compared with placebo. In Part B, a term for treatment by-baseline interaction will be included as independent variable in the model for KCCQ-TSS.

Model summary in Part A:

- 6MWD change from baseline at 16 Weeks:

$$\begin{aligned} E[CHG_{6MWD} | BASE_{6MWD}, TRT] \\ = \beta_0 + \beta_1 * BASE_{6MWD} + \beta_2 * STRATA + \beta_3 * TRT \end{aligned}$$

- KCCQ-TSS change from baseline at 16 Weeks:

$$\begin{aligned} E[CHG_{KCCQ-TSS} | BASE_{KCCQ-TSS}, TRT] \\ = \beta_0 + \beta_1 * BASE_{KCCQ-TSS} + \beta_2 * STRATA + \beta_3 * TRT \end{aligned}$$

Model summary in Part B

- 6MWD change from baseline at 24 Weeks:

$$\begin{aligned} E[CHG_{6MWD} | BASE_{6MWD}, TRT] \\ = \beta_0 + \beta_1 * BASE_{6MWD} + \beta_2 * STRATA + \beta_3 * TRT \end{aligned}$$

- KCCQ-TSS change from baseline at 24 Weeks:

$$\begin{aligned} E[CHG_{KCCQ-TSS} | BASE_{KCCQ-TSS}, TRT] \\ = \beta_0 + \beta_1 * BASE_{KCCQ-TSS} + \beta_2 * STRATA + \beta_3 * TRT + \beta_4 \\ * BASE_{KCCQ-TSS} * TRT \end{aligned}$$

Where TRT indicates randomized treatment group; STRATA indicates neutrophil baseline strata; BASE_{6MWD} and CHG_{6MWD} indicates baseline and change from baseline in 6MWD, respectively; and BASE_{KCCQ-TSS} and CHG_{KCCQ-TSS} indicates baseline and change from baseline in KCCQ-TSS, respectively.

Subgroup analyses will be performed for both primary endpoints.

Primary Efficacy Objectives Related Estimands:

Part A:

Treatment: Treatment with 2.5 mg or 5 mg AZD4831 compared to placebo, administered in addition to optimal back-ground therapy for co-morbidities.

Population: Patients that fulfill all of the inclusion criteria, none of the exclusion criteria and have available measurements of the efficacy endpoint at baseline and 16 weeks.

Endpoint: Change from baseline to 16 weeks in KCCQ-TSS and 6MWD.

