4.6 Safety Analyses

The domain safety covers exposure, adverse events, clinical laboratory, vital signs, and electrocardiogram (ECG).

Tables, figures, and listings are provided for SAS unless otherwise stated. All tabulations of safety data (AEs, laboratory parameters, vital signs, and ECG) will be based on both the On-treatment period and On-study period respectively unless otherwise stated.

The analyses will be presented for AZD4831 2.5mg, AZD4831 5mg, AZD4831 Total (pooled treatment groups AZD4831 2.5mg and 5mg) and placebo, unless otherwise stated.

Safety estimand definition

The aim with the analyses of safety data is to assess the general safety objective; this will be done for a hypothetical scenario where study treatment is not prematurely discontinued. Two different handling of intercurrent event strategies are considered complementary to assess this hypothetical scenario for all safety endpoints:

- On-treatment; unbiased under the assumption that censoring following premature treatment discontinuation is non-informative. Note that this approach could also be described as handling premature treatment discontinuation with a hypothetical strategy.
- On-study; unbiased under the assumption that the risk for an event is independent of continued treatment. Note that this approach could also be described as handling premature treatment discontinuation with a treatment policy strategy.

Hence, the general safety objective will be assessed through two complementary estimands with respect to handling of the intercurrent event of premature discontinuation of study treatment, defined by the following attributes:

- **Population:** Subjects with an established diagnosis of HF with LVEF > 40%, as defined by the inclusion and exclusion criteria, who have received at least one dose of IP. Implemented using the safety analysis set.
- **Treatment:** Actual treatment group (i.e., not necessarily the treatment a subject was randomised to), AZD4831 2.5mg/5mg or placebo.
- **Intercurrent events:**
 - Premature study treatment discontinuation: All analyses will be provided using two complementary strategies:
 - Hypothetical strategy: Premature study treatment discontinuation cannot occur, implemented by censoring data after premature study treatment discontinuation + 14 days, using the On-treatment analysis period (Section 3.3.1.5).

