4.6.2.2 Presentation

For all AE tables, unless otherwise stated, the number and percentage of subjects experiencing an event along with Kaplan-Meier percentages at 16 and 48 weeks will be presented for all treatment groups. In addition, KM% differences and HR together with 95% confidence intervals will be presented for the comparisons of each active treatment group to placebo. Percentages will be calculated with number of subjects in SAS as denominator, and subjects will only be counted once per category, regardless of the number of AEs satisfying each condition.

Tables where AEs are presented by SOC and PT will be sorted by international order for SOC and alphabetical order for PT.

In addition, KM% estimates of the cumulative distribution function of subjects with AEoSIs will be plotted comparing all treatment groups. Overall summary of AEs

The following categories will be presented in the overall summary:

- any AE,
- any SAE,
- any SAE with outcome death,
- any AE leading to discontinuation of IP, and
- any AE possibly related to IP (as assessed by investigator).

Any AE leading to discontinuation of IP category will only be analysed for the On-treatment period.

By SOC and PT

Separate AE tables by SOC and PT will be presented for the following categories:

- any AE,
- AEs possibly related to IP,
- AEs leading to discontinuation of IP,
- AEs by cumulative maximum intensity (any, moderate or severe, severe),
- any SAE,
- SAE with outcome death, and

- AEs of special interest.

Most common AEs

A table of the number and percentage, and KM% at 16 and 48 weeks of the most common adverse events by PT (frequency of > 5%). This table will be sorted by decreasing frequency in AZD4831 5mg arm.

Most common non-serious AEs

A table of non-serious AEs occurring in more than 5% of subjects in any treatment group will be presented, by SOC and PT.

AEs of special interest

A mapping of the AEoSIs to Preferred terms will be presented.

For each of the SOC Infections and infestations and the HLGT Fungal infectious disorders, an overall summary, and any AE and SAE by PT will be presented. In the overall summaries, AEs by cumulative maximum intensity (any, moderate or severe, severe) will be presented in addition to categories described under Overall summary of AEs.

Skin reactions will be presented by a summary of the following categories of skin reactions:

- any skin reaction/rash

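### If 5 mg is closed in only one country or ethnic group, the planned whole-arm comparisons of single doses become confounded by cohort, and the 5 mg versus 2.5 mg rash gradient would probably be attenuated

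*Protocol*

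**What the plan says.** Protocol 1.1 plans that "approximately 660 participants will be randomised in 3 treatment groups in 1:1:1 allocation". It then provides for the case where randomisation to 5 mg "is stopped during the study in either the whole study or in a country or specific ethnic population due to safety"; in that event "the remaining participants in that cohort would be randomised at a 2:1 ratio to AZD4831 2.5 mg or matching placebo". Protocol 6.3 repeats the rule and adds that "The randomisation will be stratified by neutrophil count in both Part A and Part B". No other stratification factor is named.

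For safety, SAP 4.6 states: "The analyses will be presented for AZD4831 2.5mg, AZD4831 5mg, AZD4831 Total (pooled treatment groups AZD4831 2.5mg and 5mg) and placebo, unless otherwise stated". SAP 4.6.2.1 bases the hazard ratios on a Cox model whose only factor is treatment group. SAP 4.6.2.2 uses the full safety analysis set as denominator and says "KM% differences and HR together with 95% confidence intervals will be presented for the comparisons of each active treatment group to placebo".

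For efficacy, protocol 9.4.2.1 says "For Part A, both single doses alone, and both doses pooled, will be compared with placebo". Its Part A models contain baseline, neutrophil stratum and treatment only.

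The one SAP rule for a stopped 5 mg arm is in 3.3.4. It moves the formal test from pooled doses versus placebo to 2.5 mg versus placebo, and it does not say whether a partial closure triggers the move.

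On the use of the results, protocol 3.1 says: "The dose in Part B will be the dose with optimal risk-benefit profile based on the data in Part A".

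**The concern.** A partial closure breaks the link between arm and randomised comparability. After it, the 5 mg arm stops receiving one cohort while the other two arms go on receiving it, and 2.5 mg receives it at twice the previous rate. A whole-arm comparison then mixes the dose effect with the difference in cohort make-up. Neither the safety nor the single-dose efficacy analyses contain a term that would separate the two.

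The reason for a closure gives the likely direction. A cohort closed because of rash is one in which rash is suspected to be more frequent. Moving it out of 5 mg and into 2.5 mg lowers the crude rate at 5 mg and raises it at 2.5 mg through composition alone. Protocol Table 3 lists both the selective stopping of 5 mg and the Part B dose selection as mitigations for rash. Using the first would disturb evidence used for the second: 5 mg could look safer relative to 2.5 mg than it is.

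**Working it through.** **Inputs from the documents**
- 660 randomised 1:1:1, so 660/3 = 220 per arm with no closure. This agrees with the 220 per arm in the protocol synopsis.
- After closure, within the cohort: 5 mg goes from 1/3 to 0, 2.5 mg from 1/3 to 2/3, and placebo stays at 1/3.
- Rash at 5 mg (protocol 4.3): 2/12 = 16.7% in the Japanese and Chinese volunteer study, and 1/27 = 3.7% in the Phase 2a patients.

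**Assumptions not in the documents**
- The closed cohort is a share *s* of the trial and is closed after a fraction *f* of its recruitment.
- The two early rates carry over to Part A, 16.7% in the closed cohort and 3.7% elsewhere.
- The 2.5 mg risk is half the 5 mg risk in both groups, so the true ratio is 2.0.

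**Formulas**
- Cohort at 5 mg = 660·s·f/3
- Cohort at 2.5 mg = 660·s·f/3 + 660·s·(1−f)·2/3
- Cohort at placebo = 660·s/3
- Outside the cohort, each arm = 660·(1−s)/3
- Crude arm risk = size-weighted mean of cohort and non-cohort risk

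**Worked case: s = 20%, f = 50%**
- Cohort: 22 at 5 mg, 22 + 44 = 66 at 2.5 mg, 44 at placebo. Outside: 176 per arm. Arm totals: 198, 242, 220.
- Cohort share: 22/198 = 11.1% of 5 mg, 66/242 = 27.3% of 2.5 mg, 44/220 = 20.0% of placebo.
- Crude rash at 5 mg: (22 × 0.1667 + 176 × 0.0370)/198 = 5.1%.
- Crude rash at 2.5 mg: (66 × 0.0833 + 176 × 0.0185)/242 = 3.6%.
- Apparent ratio 1.42. Without closure: 6.3% versus 3.1%, ratio 2.00.
- Restricted to participants for whom 5 mg was open: 198 per arm, 5.1% versus (22 × 0.0833 + 176 × 0.0185)/198 = 2.6%, ratio 2.00.

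**Crude 5 mg : 2.5 mg rash ratio when the true ratio is 2.0**

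| Cohort share | f = 10% | 25% | 50% | 75% |
|---|---|---|---|---|
| 5% | 1.55 | 1.61 | 1.74 | 1.86 |
| 10% | 1.29 | 1.39 | 1.58 | 1.78 |
| 15% | 1.13 | 1.26 | 1.48 | 1.73 |
| 20% | 1.02 | 1.17 | 1.42 | 1.69 |
| 30% | 0.89 | 1.07 | 1.37 | 1.67 |

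The restricted comparison returns 2.00 in every cell. If the true ratio is the same in both groups, the crude ratio scales with it. Over the 5-30% shares, a true ratio of 4.0 appears as 1.78 to 3.73, and a true ratio of 1.33 as 0.59 to 1.24.

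**Other contrasts in the worked case**
- 2.5 mg versus placebo is also unbalanced (27.3% against 20.0% cohort). The crude 2.5 mg rate is 3.6% instead of 3.1%.
- Pooled active holds (22 + 66)/440 = 20.0% cohort, the same as placebo. It stays 2:1 before and after closure.

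**The case against.** Several points on the other side carry weight.

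- **The effect on dose choice cannot be seen.** Protocol 4.3 rests the Part B dose on the totality of Part A data. SAP 5 leaves the Unblinded Review Committee's scope of analysis to its own charter, and SAP 3.1 leaves the skin-reaction reviews to the Data Review Committee's charter. Neither was supplied, and either might call for cohort-level or concurrent comparisons. This stands, and it limits the claim to what the SAP's own outputs would show.
- **Ethnic origin is not established as the risk factor.** The 2/12 and 1/27 come from healthy volunteers and from patients who were up-titrated. Fisher's exact p is about 0.22. This stands, so the rates serve as illustration only.
- **The cohort might be small.** SAP 4.1.3.1 lists 18 countries, with Japan and Taiwan the only East Asian ones. Under equal recruitment (an assumption), one country is 1/18 = 5.6% and both are 11.1%. The crude ratio would then be 1.58-1.71 or 1.36-1.55 for closure at 25-50%. This reduces the size but not the direction.
- **The imbalance would be visible.** The SAP tabulates recruitment by country and Asian subgroup by arm, lists skin reactions and requires narratives. Protocol 9.4.3 makes the safety analyses descriptive, without p-values. A careful reader could notice the shift, but nothing adjusts for it. The SAP's subgroup analyses by race and region (4.2.1.7) are for efficacy endpoints.
- **Cases that trigger a closure remain in the 5 mg arm.** They may offset part of the dilution, but that is a second bias and not a correction.
- **It may never happen.** The point depends on a partial closure, and the SAP's amendment history through version 4 mentions none. If none occurs, the added rule changes nothing.

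**Conclusion.** The gap is real. The protocol foresees a partial closure of 5 mg, but the SAP has no concurrent or cohort-stratified analysis for the single-dose comparisons that such a closure would confound. For rash, the expected direction is attenuation of the 5 mg versus 2.5 mg gradient, provided the closed cohort has the higher risk. With a true ratio of 2.0, the illustration gives about 1.3-1.9 for a 5-10% cohort (closure after 10-75% of its recruitment) and about 1.1-1.5 for a 15-30% cohort (closure after 25-50%). Cohort share, closure time, both rates and the halving at 2.5 mg are all assumptions. No size is claimed for efficacy.

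A reader might infer that the gradient would be masked. The figures do not show that in general. At a true ratio of 2.0, 5 mg still looks worse in every cell of the table except a 30% cohort closed after 10% of its recruitment. Reversal otherwise needs a shallower true gradient. A reader might also infer that the Part B dose choice would be wrong, or that ethnic group drives rash. The documents support neither.

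**What to change.** Keep the tables on the whole safety analysis set, so that every exposed participant is reported. Add a rule to the SAP that applies if 5 mg is closed in part of the trial:

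- **5 mg versus 2.5 mg and 5 mg versus placebo**, for rash and other adverse events (SAP 4.6) and for the single-dose efficacy comparisons (SAP 4.2): add an analysis restricted in all arms to participants randomised while 5 mg was open to their cohort. Alternatively, stratify by closure cohort and open/closed period.
- **2.5 mg versus placebo:** stratify by the same factors, including where SAP 3.3.4 makes it the formal test. State in 3.3.4 whether a partial closure triggers that switch.
- **Pooled active versus placebo:** no adjustment for cohort balance is needed. Note beside it that the dose mix in the closed cohort shifts towards 2.5 mg.
- **Committee outputs:** confirm that the Unblinded Review Committee and Data Review Committee charters use the same rule.

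Cost: one flag from the randomisation system (5 mg open or closed to the participant's cohort at randomisation), a few extra outputs, and some loss of precision in the restricted comparisons. In the worked case, these would leave out 242 − 198 = 44 participants at 2.5 mg and 220 − 198 = 22 on placebo.
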